4.5 Demographic and Other Baseline Characteristics

4.5.1 Demographic and Baseline Characteristics

Demographic and baseline characteristics will be summarized for all study populations by treatment group. Summaries will include descriptive statistics for continuous and categorical measures. Patient characteristics to be presented include:

- Age
- Age Group
 - 6 months to <18 years, ≥18 years
 - 6 months to <7 years, 7 years to <13, ≥13 years
 - 6 months to <12 years, 12 years to <18 years, ≥18 years
- Gender
- Race
- Ethnicity
- Baseline Pathogen
- Ear wick placement

Age will be calculated as the time in years between a patient's birth date and the date of informed consent.

Patient listings of demographic and baseline characteristics will be provided.

4.5.2 Medical History

General medical history will be coded using the Medical Dictionary for Regulatory Activities (MedDRA) version 20.0. A summary of medical history by system organ class

(SOC) and preferred term (PT) will be presented as frequencies and percentages for each treatment group and overall.

Medical history will also be listed. The listing will be sorted by treatment group, patient identification number, SOC, PT, and reported term.

A separate listing will be presented for AOE history.

4.5.3 Prior and Concomitant Medications

Prior and concomitant medications (CMs) will be coded using the World Health Organization (WHO) Drug dictionary version Q4 2016 (B2 Enhanced, Dec 1st, 2016). Medications and all information collected will be reported via the eCRF.

For any recorded medication other than study medications, medication start and stop dates will be compared to the date of first dose of study medication to allow medications to be classified as either prior only, both prior and concomitant, or concomitant only.

Medications that start and stop prior to the first dose of study medication will be classified as prior only. If a medication starts before the first dose of study medication and stops on or after the first dose of study medication then the medication will be classified as both prior and concomitant. Medications will be classified as concomitant only if they started on or after the first dose of study medication.

Partial date rules for flagging prior and concomitant medications will follow the rules detailed in the AEs. In case of missing dates, a medication will be considered as concomitant only.

A summary of CMs will be presented as frequencies and percentages by Anatomical Therapeutic Chemical (ATC) Class 1 and preferred term for each treatment group and overall.

CMs will be also tabulated by treatment group and type of pain treatment. Each CM will be categorized into one of 5 categories:

1. Acetaminophen (Paracetamol)
2. Ibuprofen
3. Medication Containing Codeine
4. Other Pain Treatment
5. Other Medication Than Pain Treatment

The proportion of patients that took each type of pain treatment will be compared between treatment groups using Pearson's Chi Squared tests for independence. If the concomitant medications analysis by type of pain treatment shows difference between treatment groups, subgroup analyses by type of pain treatment will be performed on efficacy results as post-hoc

analyses. If less than 80% of the expected counts are less than 5 or at least one category has no patients in a treatment group, then Fisher's exact test will be used.

A listing of CMs and prior medications will also be provided.

CMs will be considered rescue medication if they meet both of the following criteria:

- Any otic or systemic treatment administered for signs/symptoms of otitis externa of the evaluable ear (Note – topical antibiotics applied in the non-evaluable ear are NOT considered to be rescue medications)
- Started after Visit 1 but before End-of-study visit (Note – antibiotics given after End-of-study visit are NOT considered rescue medications)

The number of patients taking rescue medications will be tabulated by treatment group. A listing will also be provided.

Effective concomitant therapy (ECT) will be defined as any antibacterial or antiseptic treatment administered for reasons not associated with acute otitis externa.

The number of patients taking ECTs will be tabulated by treatment group.

Type of pain treatment and medications that qualify as rescue medications or ECTs will be determined during the blinded data review before database lock.

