## 6.7 Concomitant Medications

Any medication the patient takes other than the study medication specified in the protocol is considered a concomitant medication. This includes prescribed medications, over-the-counter medications, herbal remedies, vitamins, supplements etc. All treatments must be recorded in the EDC in the concomitant medication page.

At Visit 1, patients will be asked what medications they are currently taking or have taken during the last 30 days. At Visits 2, 3, and 4, patients will be asked what concomitant medications they are currently taking or have taken since the last visit, including medications for pain.

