4.4 Analysis Populations

There will be 6 populations defined for this study: Safety, Clinical intent-to-treat (CITT), Microbiological intent-to-treat (MITT), MITT-PA/SA, CPP, and MPP.

The **Safety population** will include all patients who received any study medication.

The **CITT population** will include all patients who were randomized.

The **MITT population** will include all CITT patients whose Visit 1 microbiological culture yields 1 or more pathogens, as defined in Section 4.7.2.

The **MITT-PA/SA population** will include the pathogen positive subset of the CITT population which includes all patients who received study medication and had culture positive for *P. aeruginosa* and/or *S. aureus* at baseline in the evaluable ear.

The **CPP population** will include all CITT patients who:

- Satisfied all inclusion and exclusion criteria;
- Had analysis results from Visit 1 otorrhea sample;
- Did not receive any prohibited concomitant medications. Note if a patient receives prohibited medication on or after receiving rescue medication and does not have any other major protocol deviations, the patient will be included in the CPP;
- Did not have any other major protocol violations;
- Completed Visit 3 and Visit 4 (unless the patient was deemed a clinical failure at an earlier visit than Visit 4);
- Had compliance rates between 80% and 120% as defined in Section 4.6 (patients who are deemed Clinical Failures are to be included if they had compliance rates between 80% and 120% during the first 3 days of study treatment); and
- Received at least 4 doses of study medication during the first 72 hours.

The **MPP population** will include all CPP patients whose Visit 1 microbiological culture yields 1 or more pathogens and who had microbiological results (when patient has material to culture) from Visit 2 and/or Visit 4 unless the patient was deemed a clinical failure at an earlier visit than Visit 4.

For the CITT, MITT and MITT-PA/SA populations, the treatment group of a patient will be determined by the treatment group to which the patient was randomized.

Effective Date: [REDACTED]
Related to: [REDACTED]

CONFIDENTIAL

Project Document Version No. 2.0
Project Document Effective Date: Date of last signature

Page 12 of 34

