- Presumed Eradication if the culture does not show growth of any pathogen or if there is no material to culture and the Overall Clinical Outcome is Clinical Improvement or Clinical Cure as defined above;
- Presumed Persistence if the Overall Clinical Outcome is Clinical Failure but no culture result is available from Visit 4;
- Recurrence if there is no material to culture, the Overall Clinical Outcome is Clinical Failure, and the Overall Clinical Outcome at Visit 3 is Clinical Cure;
- Superinfection if a pathogen not present at Visit 1 and Visit 3 is now present;
- Indeterminate if none of the above definitions are met and the bacteriologic response cannot be determined.

The above rules will be used for microbiological outcome summaries for the patients in the CITT and CPP populations that have no pathogen at Visit 1, since microbiological response cannot be calculated without any pathogen at Visit 1.

If Overall Clinical Outcome at Visit 3 is Clinical Failure (whether or not the patient discontinues prematurely) and no bacterial culture is performed at Visit 3, the bacteriologic response at Visit 3 will be Presumed Persistence. If Overall Clinical Outcome at Visit 4 is Clinical Failure and no bacterial culture is performed at Visit 4, the bacteriologic response at Visit 4 will be Presumed Persistence.

Therapeutic cure: TSSS (otalgia+edema+otorrhea) of 0 and bacteriological response of eradication or presumed eradication

Therapeutic failure:

- Positive culture for pathogens (independent of TSSS) or
- Negative culture or presumed eradication with TSSS>0

If a patient took rescue medication prior to Visit 3, the response will be considered a failure at Visit 3. Similarly, if patient took rescue medication prior to Visit 4, the response will be considered a failure at Visit 4.

Therapeutic response will be summarized by treatment group and visit in terms of proportion of cures and failures at each visit.

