4.8.2 Adverse Events

Adverse events will be coded using the MedDRA Version 20.0. Adverse events will be tabulated by body system, preferred term, and treatment group.

Treatment-emergent adverse events (TEAEs) will be tabulated for the following subsets:

1. All TEAEs;
2. Related TEAEs;
3. Serious adverse events (SAEs);
4. Related Serious TEAEs;
5. Adverse events leading to study discontinuation;
6. Adverse events leading to discontinuation of study medication;
7. Adverse events resulting in death;

Tabulations of AEs by body system, preferred term, treatment group, and severity, and by body system, preferred term, treatment group, and relationship to study medication will also be provided.

The data will be displayed as number of subjects experiencing the AE, percentage of subjects, and number of AEs. All AE summaries will provide the number of patients reporting at least 1 AE and the total number of events reported.

General Rules for Adverse Events

1. An AE will be considered as treatment-emergent if it begins on or after the first study drug dosing or that worsens in severity after at least 1 dose of study drug has been administered. In case of insufficient information to determine if the event occurred before, during or after study drug dosing, the AE will be considered as treatment-emergent.

The imputation method for the handling of missing or partial dates will be as follows:

Start dates

- If the day is missing, but month and year are present and the same as the month and year of the first dose of study drug, then day will be set to the same day as the start of study drug. Otherwise, this will be imputed as the first day of the month.
- If the month is missing, but year is present and the same as the year of the first dose of study drug, then month will be set to the same month as the start of study drug. Otherwise, this will be imputed as January.
- If the year is missing, the event will be considered as treatment emergent and the start date will be imputed as the date of first treatment.

Stop dates

- If the day is missing, this will be imputed as the last day of the month, or the last day of participation in the study if the AE end month is the same as the last date of participation in the study.
- If the month is missing, this will be imputed as December, or the last month of participation in the study if the AE end year is the same as the last date of participation in the study

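### SAP 4.5.3 classifies incompletely dated medications without using a known stop date, so a drug that ended before first dose can be counted as on-study

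*SAP*

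**What the plan says.** SAP 4.5.3 sorts medications into prior only (start and stop both before first dose), both prior and concomitant, and concomitant only. The last class depends on the start date alone: "Medications will be classified as concomitant only if they started on or after the first dose of study medication".

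For incomplete dates, the same section says: "Partial date rules for flagging prior and concomitant medications will follow the rules detailed in the AEs". It then adds: "In case of missing dates, a medication will be considered as concomitant only". It does not say whether this means the start, the stop or both.

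The borrowed rules are in SAP 4.8.2. If the start day is missing and the month and year match first dose, "then day will be set to the same day as the start of study drug". In any other month the start becomes the 1st of that month. A missing month becomes the first-dose month if the year matches. A missing year gives the date of first treatment. A missing stop day becomes the last day of the month, or the last day of participation if that falls in the same month.

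Three other provisions use medication timing:
- A rescue drug must satisfy, among other things, "Started after Visit 1 but before End-of-study visit" (SAP 4.5.3).
- On the primary endpoint, "If a patient took rescue medication prior to Visit 3, the response will be considered a failure at Visit 3" (SAP 4.7.2).
- Membership of the CPP population, and so of MPP, requires that the patient "Did not receive any prohibited concomitant medications" (SAP 4.4).

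**The concern.** Moving an unknown start to first dose is cautious for adverse events, because it errs towards calling an event treatment-emergent. For medications it has no such merit. It can override a recorded fact (the drug had already stopped) and produce a record whose start is later than its stop.

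Such records are foreseeable. Protocol 6.7 asks at Visit 1 about drugs taken in the previous 30 days, including those already stopped. Protocol 6.7.3 lets patients on ibuprofen or other anti-inflammatories enrol if they stop at enrolment.

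The flag has a direct use. SAP 4.5.3 tabulates concomitant medications by type of pain treatment, with ibuprofen as its own category, and compares the arms by chi-squared test. If the arms differ, efficacy subgroup analyses by pain treatment will be performed. The blinded review settles the type of pain treatment; the text does not say that it corrects the timing flag.

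The documents give no other date convention for medications. It is therefore unclear which dates the reviewers of rescue and prohibited drugs should use.

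**Working it through.** The plan states no figure on this point, so there is none to reproduce. The check applies the written rules literally.

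**Single records.** First dose 20 June; ibuprofen stopped 10 June.
- Start recorded as June, day missing: the month matches, so the start is imputed to 20 June. This is ten days after the recorded stop. Start ≥ first dose, so the drug is concomitant only.
- Start recorded as May, day missing: imputed to 1 May. Start and stop both precede first dose, so the drug is correctly prior only.
- Start wholly missing: concomitant only, under both the missing-date sentence and the missing-year rule.

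**How often, among incompletely dated records.** Inputs: the 30-day look-back (Protocol 6.7), the start and stop rules (SAP 4.8.2) and the classes (SAP 4.5.3). Assumptions, not in the documents: first dose on each of 365 days with equal weight; true start a = 1 to 30 days before first dose; true stop b = 1 to a days before; last participation on Day 16. That gives 30 × 31 / 2 = 465 start–stop pairs per first-dose date. In truth every one of them is prior only.

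| What is missing | Prior only | Both | Concomitant only |
|---|---|---|---|
| Start day; stop known | 66.8% | – | 33.2% |
| Stop day; start known | 35.1% | 64.9% | – |
| Both days | 35.1% | 31.7% | 33.2% |
| Whole start date; stop known | 0% | – | 100% |

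In the first row, every one of the 33.2% has an imputed start later than its recorded stop. This is the clear error. In the second and third rows, a stop recorded only to the month of first dose does not itself show that the drug ended earlier. Those records call for a query more than a rule.

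**Conditional check: rescue timing.** Suppose imputed dates were used for the rescue test, and the day is missing for a drug truly started after Visit 1. First dose is given at Visit 1, so a start in the Visit 1 month is set to the Visit 1 date and fails the after-Visit-1 criterion.
- True start on Days 2–8: 86.8% dated to Visit 1.
- True start on Days 2–17: 72.1% dated to Visit 1.
- True start on Days 9–16, with Visit 3 on Day 8: 62.2% dated to Visit 1, and a further 19.7% dated after Visit 1 but before Visit 3.

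The first-dose date is not universal. With Visit 1 on 28 June and a rescue start recorded only as July, the imputed date is 1 July, which passes.

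**The case against.** A reader might infer that drugs stopped before Visit 1 automatically become prohibited on-study drugs, and that rescue drugs are dated to Visit 1 and so escape the primary-failure rule. The documents do not support this.

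- SAP 4.5.3 introduces the borrowed rules for flagging prior and concomitant status only. It assigns rescue and effective-concomitant-therapy decisions to the blinded data review.
- Major deviations and analysis sets are also settled at a blinded review (SAP 4.3.2). A reviewer who sees a recorded stop before first dose has no reason to find on-study use. Any such error would reach CPP and MPP, not the primary MITT-PA/SA population.
- Missing data are to be discussed with the investigator and queried if necessary (Protocol 9.2). At Visits 2, 3 and 4, "patients will be asked what concomitant medications they are currently taking or have taken since the last visit" (Protocol 6.7). The diary records pain-medication use, with the time and date of the assessment (Protocol 7.1.1.6). Few rescue drugs should lack a start day in so short a trial.
- Other routes already lead to primary failure: stopping study medication at the no-improvement visit, discontinuation for lack of efficacy, and any TSSS above 0. A rescue drug mis-dated to Visit 1 changes the result only if the patient otherwise met the cure definition at Visit 3.
- A single misclassified patient can be made to cross 0.05 in a chosen example (116/150 against 100/150 gives p = 0.040; 115/150 gives p = 0.055). That would be true of any misclassification and says nothing particular about this rule.

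All of this stands, and it limits the size of the point. It does not answer the defect in the flag itself: the written rule ignores a known stop and can generate impossible dates. Nor does it tell the blinded review which dates to use.

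**Conclusion.** The point holds as a defect in the prior/concomitant classification. Under the uniform-timing assumptions, about one third of stopped prior drugs with a missing start day and a known stop are wrongly called concomitant only, and all of them if the start date is wholly missing. The number of patients affected is unknown, because the documents do not say how many incompletely dated records to expect.

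The direct effect is on the concomitant-medication tables and the pain-treatment comparison. The misplaced drugs were taken before treatment, so the error should be balanced between randomized arms on average. It adds noise to that comparison and may dilute a real difference, rather than favour one arm. The subgroup analyses that it triggers are labelled post hoc.

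Effects on rescue timing, and so on the primary endpoint, and on CPP/MPP membership are possible only if imputed dates were carried into the blinded review. If that happened, one changed primary outcome would be worth 1/150 = 0.67 percentage points in an arm of 150, or 1/75 = 1.33 points in the arm of 75. This part is an ambiguity to close, not a demonstrated error.

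**What to change.** Amend SAP 4.5.3 to state:

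1. If a stop date, complete or partial, shows that the drug ended before first dose, the drug is prior only. An imputed start may never be later than a known stop.
2. A drug first reported at Visit 1 with an unknown start is prior, or both prior and concomitant if it is ongoing.
3. Imputed dates are used only for the prior/concomitant flag. The blinded review decides the timing of rescue, effective concomitant therapy and prohibited drugs from recorded dates, query responses and visit-level information, such as the visit of first report where this is captured.

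I would not add an automatic rule that a drug first reported at Visit 3 started before Visit 3. A drug prescribed at that visit after the assessment would then be scored as earlier rescue. Nor would I add a default that scores unresolved cases as failures, since that choice is open to dispute.

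The cost is minor SAP wording and programming before database lock. No new data are needed for items 1 and 3; item 2, and the visit of first report in item 3, depend on that visit being identifiable in the EDC.

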4.6 Treatment Compliance

Study medication compliance will be assessed during the first 3 days of the treatment period, during the treatment period (first 7 days), and during the overall study.

Treatment Compliance is calculated as:

$$\frac{\text{Number of doses taken}}{\text{Expected number of doses taken}} \times 100\%$$

The number of doses taken is the number of doses the patients actually took during a given period.

The number of expected doses taken is the number of doses the patient was expected to take during that period. It is calculated based on the patient's duration of participation in the study. If a patient completes treatment, 6 doses are expected in the first 3 days of treatment. For the treatment period, 14 doses are expected. If a subject does not complete treatment in the treatment period (first 7 days), then the expected number of doses for the overall study will be twice the number of days that the patient took study medication. If a patient discontinues early, the expected number of doses is based on the time of early discontinuation.

██
Effective Date: ███
Related to: ███

CONFIDENTIAL

Project Document Version No. 2.0
Project Document Effective Date: Date of last signature
Page 15 of 34

Percent compliance will be summarized by treatment group. Compliance will also be summarized by treatment group and age group (6 months to <18 years and ≥ 18 years).

Compliance will be listed for each patient.

Patients will be considered “compliant” if their percent compliance is between 80% and 120%. The proportion of patients who were compliant and non-compliant during the treatment period and during the first 3 days of the treatment period will be tabulated by treatment group.

4.7 Efficacy Evaluation

4.7.1 Hypothesis

This study is designed to test for superiority. The primary analyses will compare the combination treatment group with each component alone using the MITT-PA/SA population. The null hypotheses will be that there is no difference between Ciprofloxacin plus Fluocinolone acetonide and Ciprofloxacin alone and that there is no difference between Ciprofloxacin plus Fluocinolone acetonide and Fluocinolone acetonide alone. The alternative hypothesis will be that there is a difference. Symbolically, this is expressed as follows:

$$H_0: p_{\text{Ciprofloxaci plus Fluocinolone acetonide}} = p_{\text{Ciprofloxacin}}$$
$$H_a: p_{\text{Ciprofloxaci plus Fluocinolone acetonide}} \neq p_{\text{Ciprofloxacin}}$$

and

$$H_0: p_{\text{Ciprofloxaci plus Fluocinolone acetonide}} = p_{\text{Fluocinolone acetonide}}$$
$$H_a: p_{\text{Ciprofloxaci plus Fluocinolone acetonide}} \neq p_{\text{Fluocinolone acetonide}}$$

where p is the proportion of patients with therapeutic cure.

A two-sided chi-square (or χ^2) test with $\alpha=0.05$ will be used to test this hypothesis and conduct the between-treatment comparison. This approach will also be used for other (secondary) efficacy endpoints as described in Section 2.

The principal secondary analysis will also compare the combination treatment group with each component alone. The null hypothesis is that there is no difference in time to end of pain between the combination and the components alone. The alternative hypothesis is that there is difference in time to end of pain between the combination and the components alone.

The comparison will be made using the log-rank test stratified on age (6 months to <18 years versus ≥ 18 years) with $\alpha=0.05$.

Effective Date: [REDACTED]
Related to: [REDACTED]

CONFIDENTIAL

Project Document Version No. 2.0
Project Document Effective Date: Date of last signature
Page 16 of 34

Only assessments in the evaluable ear will be used for efficacy analyses.

